1. INTRODUCTION/ REVIEW

Prostate cancer (PCa) is the second most common neoplasm diagnosed in men with an estimated 1.4 million diagnoses and 375,000 deaths worldwide in 2020 [1].

For localized prostate cancer (PCa), active surveillance (AS) or whole gland treatment (ie, radical prostatectomy [RP] and radiotherapy) are considered standard treatment options. Unfortunately, treatment-related morbidity is high. [2]

The ProtecT trial showed urinary incontinence rates of 3% and 20% and erectile dysfunction rates of 66% and 79% for radiotherapy and radical prostatectomy, respectively [2]. Radiotherapy can also cause rectal problems with a small increased risk of radiotherapy-induced secondary malignancy. [3]

Consequently, over the past few years, there has been a notable escalation in scholarly attention towards the implementation of focal therapeutic interventions for patients diagnosed with low- and intermediate-risk prostate cancer (PCa).

This tissue-preserving strategy has at its core the reduction of treatment-related toxicity by minimizing damage caused to the prostate and adjacent structures while attempting to retain the benefits of treating cancer. [4]

The rationale of focal therapy (FT) is based on the theory that the largest lesion with the highest grade, the so-called “index lesion,” determines the risk of metastases and thus the patient’s prognosis [5, 6].

FT involves ablating only the index lesion, thereby minimizing damage to collateral tissue such as neurovascular bundles, external urinary sphincter, bladder neck and rectum. [4]

Over the past few years, different types of energy sources in FT have been studied. These consist of high-intensity focused ultrasound (HIFU), irreversible electroporation (IRE), cryotherapy, photodynamic therapy (PDT), focal laser ablation (FLA) or laser interstitial thermotherapy, radiofrequency ablation (RFA), and focal brachytherapy. [7]

According to the European Association of Urology (EAU), low-risk and intermediate-risk patients may undergo local procedures using HIFU or cryotherapy within clinical trials or registries, with the aim of achieving long-term cancer control and reducing morbidity associated with surgery and radiation therapy [8].

Many groups have published limited data on outcomes following **in-bore** MRI-guided focal therapy, and many others are actively engaged or considering prospective comparative effectiveness research in this area.

Our primary objectives encompasses a thorough evaluation of the short-term oncological & functional outcomes of MRI-US or PSMA PET/CT-U/S **fusion-guided** focal laser ablation (FLA) for the treatment of a small, localized, intermediate-risk prostate cancer.

Concurrently, our secondary aim involves an assessment of the utility of multiparametric magnetic resonance imaging (mpMRI) as a diagnostic pre-treatment tool and during the post-treatment follow-up to examine the morphostructural alterations in the prostate gland resulting from FLA. Additionally, we aim to assess its reproducibility in determining the response to FLA therapy, correlating these findings with biopsy results, with the ultimate objective of establishing its predictive diagnostic value in identifying residual or recurring tumors.

2.AIM/ OBJECTIVES

To assess the effectiveness of MRI-US or PSMA PET/CT-U/S fusion-guided focal laser ablation (FLA) for the treatment of a localized, intermediate-risk prostate cancer in terms of short-term oncological & functional outcomes.

3.METHODOLOGY:

Patients and Methods/ Subjects and Methods/ Material and Methods

- **Type of Study:** Retrospective Observational Pilot study
- **Study Setting:** El-Demerdash University Hospital & Shaker Hospital.
- **Study Period:** 12 months.
- **Sample Size:** based on the rarity of cases in this study and the expensive cost of treatment, also this study is a pilot study. This protocol is exempted from sample size calculation. (No. of the patients will be 30)
- **Study Population:** Males with localized, intermediate risk prostatic adenocarcinoma
Self-funded study (the researcher himself will pay for the data collection).
The patients will not pay any fees.
- **Inclusion Criteria:**
 - Male
 - Over 45 years old
 - Prostate cancer visible on mpMRI or PSMA PET/CT and positive in the targeted biopsy.

- Gleason score 7 (ISUP grade 2/3)
- PSA 10-20 ng/mL
- Clinical stage T2b
- Refusing radical prostatectomy.
- **Exclusion Criteria:**
 - Prostate cancer invisible on mpMRI or PSMA PET/CT but positive in the systematic biopsies.
 - Presence of >2 MRI-visible lesions and positive in the biopsies.
 - Extracapsular extension
 - Seminal vesicle invasion
 - Presence of metastases detected by imaging
 - Gleason Score > 7
 - Clinical stage > T2b
 - PSA > 20 ng/mL
 - Acute urinary tract infection (UTI)
 - Severe lower urinary tract symptoms defined as an IPSS >20
 - Severe coagulation disorders
 - Inadequate compliance
 - Contraindications to MRI
 - Paramagnetic contrast agent allergy
 - Acute and/or chronic renal failure
- **Ethical Considerations:** Approval will be obtained from the ethical committee at Ain Shams University before starting the research and all patients will consent to be included in this study after explanation of the study procedures and the follow up course.
- **Study Procedures:**

The pre-procedural evaluation consisted of complete blood count, coagulation profile, urine examination and urine culture, and evaluation of post-voiding residue and uroflowmetry.

As the procedure of FLA is guided by MRI-US or PSMA PET/CT-U/S fusion images, a 3T mp MRI scan or PSMA PET/CT scan is recommended for each patient at Time 0.

On Siemens 3T MAGNETOM Skyra scanner, multiple MRI sequences will be

taken including T1, T2WI, DWI, ADC and STIR axial, coronal and sagittal images.

Injection of 2-4 ml/s of gadolinium and then post contrast dynamic imaging will be taken.

Malignant lesions will appear low signal at T2WI in comparison to the high signal intensity of the peripheral zone with restricted DWI and post gadolinium contrast enhancement.

The FLA is performed by a joint team of an expert interventional radiologist and an expert urologist on prostate MRI-US or PSMA PET/CT-U/S procedures, in a Day-Hospital setting, in a radiological interventional room or an OR.

The patient is placed in the lithotomy position, and Ciprofloxacin 500 mg is administered as antibiotic prophylaxis. The biolitec® LEONARDO® DUAL 45 Diode Laser System operating at 860 nm provides energy for the ablation.

The mpMRI data are loaded to the US system (Canon Aplio a550) via the DICOM network or a DVD and the live US image is linked with the MR image by Smart Fusion.

Under general or spinal anesthesia, thin needles (14 Gauge) are inserted transperineally under real-time US guidance fused with MRI or PSMA PET/CT. One to five needles are used depending on the lesion size and configuration because the multi-fiber approach can extend the coagulation area.

The laser light is conveyed from the source to the target through flexible, small-caliber (360 μm), flat-tipped quartz optical fibers. Multiple overlapping ablations are performed in order to assure complete coverage of the target.

The laser fiber protrudes 5 mm from the needle tip. The pull-back technique consists of pulling back the introducer by 1 cm and performing a second illumination to increase the length of the ablation area.

The laser energy is released in pulsed mode (intermittently in a series of pulses rather than continuously – 0.8 seconds on & 0.4 seconds off), with a power of 15 Watts and is activated for an average of 2 minutes (100 pulses) per ablation zone.

The laser therapy is performed entirely under US guidance fused with MRI or PSMA PET/CT for the real-time monitoring of the correct positioning of applicators and the extension of the area of damage.

At the end of the procedure, all patients are observed for a minimum period of 2 h.

An oral NSAID as anti-edema therapy is prescribed.

Patients are discharged with antibiotic therapy for 14 days, given pain-relief

drugs if needed.

A copy of the patients' files will be anonymously given to the researcher.

Follow-up with clinical evaluation performed by monthly PSA measurement until it reaches its nadir (fixed value for 2 months) and every 3 months thereafter. Repeat mpMRI is done for assessment of tissue changes as well as residual or recurrent disease after 10 days, then after 3 months, after 6 months then every 6 months thereafter. The IPSS and IIEF-5 questionnaires are submitted at 3, 6, 12 months.

Systematic and target MRI/US fusion-guided prostate biopsies are performed after 12 months or if PSA increases > 2 ng/mL, nadir PSA doubled or new suspicious lesions in mpMRI.

Failed cases are offered a further session of focal therapy if the lesion is still suitable for FLA. Radical therapy is also offered according to patient preference, or in cases of increasing volume or stage of disease or progression to high grade disease.

Treatment success is operationally defined as the absence of contrast-enhancement in MRI examinations conducted during the follow-up period, in conjunction with a negative target biopsy at the conclusion of the 12-month period and evaluation of serum PSA.

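### The pre-treatment part of the secondary aim cannot give an unselected estimate of mpMRI accuracy, because entry already requires a positive scan and a positive targeted biopsy

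*Protocol*

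**What the plan says.** The closing paragraphs of the protocol's Introduction set out a secondary aim in several parts. The first is that "our secondary aim involves an assessment of the utility of multiparametric magnetic resonance imaging (mpMRI) as a diagnostic pre-treatment tool". The sentence goes on to follow-up imaging of changes in the gland, and the paragraph ends with the goal of "establishing its predictive diagnostic value in identifying residual or recurring tumors".

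The relevant entry rules are under Methodology:

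- Study population: "Males with localized, intermediate risk prostatic adenocarcinoma".
- Inclusion: "Prostate cancer visible on mpMRI or PSMA PET/CT and positive in the targeted biopsy".
- Exclusion: "Prostate cancer invisible on mpMRI or PSMA PET/CT but positive in the systematic biopsies".
- Sample size: 30 men, without a calculation.

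Under Study Procedures, "a 3T mp MRI scan or PSMA PET/CT scan is recommended for each patient at Time 0". One of the two scans is enough; a man need not have both. For the follow-up period, the reference standard is also given there: "Systematic and target MRI/US fusion-guided prostate biopsies are performed after 12 months", or sooner if a PSA or imaging trigger is met.

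**The concern.** An assessment of a diagnostic test needs men in whom the test could be wrong. Here the entry rule uses the test result and the reference standard together, and both must be positive. Men with a suspicious scan and a negative biopsy do not enter. Men with a negative scan and cancer on systematic cores are excluded. Men without cancer are outside the study population.

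If pre-treatment agreement between mpMRI and biopsy were tabulated in this cohort, it would look excellent however good or poor mpMRI is at these hospitals. A reader could take that as evidence about the test when it reflects who was let in. A larger sample under the same criteria would not help, and no analysis plan can bring back men whom eligibility has removed.

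**Working it through.** The protocol gives no accuracy target, so there is no figure of its own to reproduce. The check is to fill the patient-level table from the eligibility rules.

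**Inputs.** N = 30 (Methodology, Sample Size). Entry needs a scan-visible lesion confirmed by targeted biopsy (Inclusion Criteria). Scan-negative men with positive systematic cores are out (Exclusion Criteria). All men have cancer (Study Population).

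**Step 1: all 30 enter on mpMRI.**

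| | Biopsy positive | Biopsy negative |
|---|---|---|
| mpMRI positive | 30 | 0 (a positive biopsy is required) |
| mpMRI negative | 0 (excluded) | 0 (no men without cancer) |

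- Sensitivity = TP/(TP+FN) = 30/30 = 100%.
- Positive predictive value = TP/(TP+FP) = 30/30 = 100%.
- Specificity = TN/(TN+FP) = 0/0, undefined.
- Negative predictive value = TN/(TN+FN) = 0/0, undefined.

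The exact 95% interval for 30/30 has lower limit 0.025^(1/30) = 0.884, so it would be printed as 88.4% to 100%. It looks informative, but the table is the same whatever the true accuracy.

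**Step 2: some men enter on PSMA PET/CT alone.** Suppose k men enter this way.

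- If they had no mpMRI, they add nothing to the mpMRI table. Study Procedures allows this, because either scan suffices at Time 0.
- If they had an mpMRI and it was negative, they are false negatives and sensitivity becomes (30 − k)/30. Negative predictive value becomes 0/k, which is zero by construction because everyone has cancer. Positive predictive value stays at 100% and specificity stays 0/0.

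**Step 3: size of the bias in sensitivity on that route.** Let Sm and Sp be the true sensitivities of mpMRI and PSMA PET/CT. Assume that every man had both scans, that a positive result on either admits him, and that the two results are independent given cancer. Then

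observed mpMRI sensitivity = Sm / [1 − (1 − Sm)(1 − Sp)].

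The protocol gives neither sensitivity, so both are assumed over a range:

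| True Sm | Sp = 0.5 | Sp = 0.7 | Sp = 0.9 |
|---|---|---|---|
| 0.5 | 0.667 | 0.588 | 0.526 |
| 0.7 | 0.824 | 0.769 | 0.722 |
| 0.9 | 0.947 | 0.928 | 0.909 |

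For example, 0.7/(1 − 0.3 × 0.5) = 0.7/0.85 = 0.824. Every entry exceeds the true value because the denominator, the chance of being seen on at least one scan, is below 1.

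**Step 4: wording of the exclusion.** It does not settle whether a negative result on one scan is enough to exclude a man who is positive on the other. If it is, Step 1 applies to men with mpMRI; if not, Step 2 does.

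**The case against.** The best reply is that the sentence speaks of utility and nowhere announces a pre-treatment sensitivity, specificity or two-by-two table. Read to its end, it may describe one before-and-after aim, with the first scan as the baseline for later changes, and the protocol does use that scan to guide the fibres. This stands in part. Lesion size, location and targeting can be reported without difficulty, and it would be wrong to infer that the study is bound to publish a spurious agreement figure, since no such analysis is written. But the sentence calls the pre-treatment role diagnostic, and this cohort cannot support that word.

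A second reply concerns lesions. The exclusion for multiple lesions applies only above two that are both visible and biopsy-positive, so an enrolled man could have a further visible lesion with negative cores, or cancer on systematic cores elsewhere. Lesion-level errors are therefore not ruled out, and a reader who infers that every accuracy figure is fixed goes too far. Any such figure would still come only from men who already have at least one visible, confirmed cancer.

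Third, the PSMA PET/CT route means that mpMRI sensitivity is not strictly fixed for the whole cohort. That is correct, and Steps 2 and 3 allow for it.

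Finally, the phrase is in the Introduction and not in the formal Aim/Objectives section, and no sample size or follow-up step depends on it. This bears on severity, not on whether the point holds.

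**Conclusion.** The point holds in a limited form. The pre-treatment diagnostic component of the secondary aim cannot yield an unselected estimate of mpMRI accuracy. At patient level, positive predictive value is 100% by construction, and specificity and negative predictive value cannot be estimated. Sensitivity is 100% by construction for men who enter on mpMRI. If men enter on PSMA PET/CT alone, it is biased upward under the Step 3 assumptions, by about 0.01 to 0.17 over the range shown (0.909 against 0.9, and 0.667 against 0.5), and it can be calculated only where those men also had mpMRI.

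A reader might infer that the whole secondary aim fails. The documents do not support that. The entry rule does not determine the result of post-treatment mpMRI against follow-up biopsy, and descriptive or planning use of the baseline scan remains open. The primary objective is untouched. Severity is minor: one component of a secondary aim.

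**What to change.** In the Introduction, delete the words that present mpMRI as a pre-treatment diagnostic tool and tidy the conjunction that follows. Describe the Time 0 mpMRI as the baseline and planning scan. Add a sentence saying that no pre-treatment diagnostic accuracy will be claimed, because entry requires an imaging-visible lesion with a positive targeted biopsy. Confine the diagnostic aim to post-treatment mpMRI against follow-up biopsy.

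The cost is an edit to the aims, with no added patients or procedures. The study gives up a claim that its design cannot support. Widening the source to all men imaged and biopsied at the two hospitals is not proposed: it would raise questions of consent and ethics scope, and the protocol does not show that scan-negative men there were biopsied, so verification bias could remain.

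### No pre-treatment IIEF-5 is specified in a study with no comparator, so change in erectile function cannot be estimated as the protocol is written

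*Protocol*

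**What the plan says.** Section 2 (Aim/Objectives) sets out to assess effectiveness "in terms of short-term oncological & functional outcomes", and the objectives at the end of Section 1 likewise count functional outcome as primary. Section 1 argues for focal therapy on tolerability: "This tissue-preserving strategy has at its core the reduction of treatment-related toxicity". As background on whole-gland treatment it cites "erectile dysfunction rates of 66% and 79% for radiotherapy and radical prostatectomy, respectively".

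On measurement, the follow-up paragraph of Section 3 (Study Procedures) states: "The IPSS and IIEF-5 questionnaires are submitted at 3, 6, 12 months". Before treatment, the same section gives this list: "The pre-procedural evaluation consisted of complete blood count, coagulation profile, urine examination and urine culture, and evaluation of post-voiding residue and uroflowmetry". It adds mpMRI or PSMA PET/CT at Time 0. One exclusion criterion uses a questionnaire score: "Severe lower urinary tract symptoms defined as an IPSS >20". No criterion refers to the IIEF-5, potency or erectile function.

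The design is labelled "Retrospective Observational Pilot study", with 30 patients and no comparison group described, and the researcher receives anonymised copies of patient files. Yet under Ethical Considerations, "all patients will consent to be included in this study after explanation of the study procedures and the follow up course".

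**The concern.** With one treated group, each man's own pre-treatment score is the only reference inside the study. The IIEF-5 first appears at month 3, after any effect of ablation would already have begun. Without an earlier value, a low score at 3, 6 or 12 months may reflect the laser treatment or a condition the man already had, and the data cannot tell these apart.

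Less harm to function is the protocol's own reason for focal therapy, so this gap touches part of the primary aim. It is also permanent: once a man has been treated without a recorded score, no later analysis can restore one. The unclear timing adds to the difficulty, because the retrospective label and the forward-looking consent statement leave open whether a baseline can still be collected.

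**Working it through.** **Where a baseline could come from.** The protocol has no figure of its own to reproduce on this point, so the first step is to go through every place where a pre-treatment value might be fixed.

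| Place in Section 3 | PSA | IPSS | IIEF-5 |
|---|---|---|---|
| Eligibility criteria | Required (inclusion range) | Required (exclusion above 20) | Not mentioned |
| Pre-procedural evaluation | Not listed | Not listed | Not listed |
| Time 0 | Not listed (imaging only) | Not listed | Not listed |
| Follow-up | Monthly to nadir, then every 3 months | 3, 6, 12 months | 3, 6, 12 months |

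PSA and IPSS are also absent from the pre-procedural list, so that list is not exhaustive and its silence alone proves little. But eligibility cannot be decided without a PSA and an IPSS, so both must exist before treatment. Nothing forces an IIEF-5 value. Urinary function also has post-void residue and uroflowmetry beforehand; erectile function has no counterpart.

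**What can be estimated.** Within-patient change at month *t* is IIEF-5 at *t* minus IIEF-5 at baseline, for *t* = 3, 6, 12. The second term is not specified, and no control group offers another contrast. What remains is the level at each visit and the change after month 3.

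**Illustration of the size.** The protocol gives no counts and no IIEF-5 cut-off for dysfunction, so the figures below are assumed; only N = 30 comes from the protocol. Let X be the men with dysfunction at 12 months, b those with it before treatment, and r those among the b who recover. Then:

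new dysfunction among men potent at baseline = (X − b + r) / (30 − b)

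For X = 15 and r = 0:

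| b | New cases / men at risk | Proportion |
|---|---|---|
| 0 | 15/30 | 50% |
| 6 | 9/24 | 38% |
| 9 | 6/21 | 29% |
| 12 | 3/18 | 17% |
| 15 | 0/15 | 0% |

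The range over all admissible b, for other values of X:

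| X | r = 0 | r = 3 |
|---|---|---|
| 9 | 0/21 to 9/30: 0–30% | 0/18 to 9/27: 0–33% |
| 15 | 0/15 to 15/30: 0–50% | 0/12 to 15/27: 0–56% |
| 21 | 0/9 to 21/30: 0–70% | 0/6 to 21/27: 0–78% |

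These are not strict bounds, since they move with the assumed X and r. They show that one and the same 12-month result is compatible with no new dysfunction and with a great deal of it.

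**The case against.** The strongest reply is that the quoted sentence belongs to a follow-up paragraph and was never meant as the full schedule. PSA and mpMRI appear there only at post-treatment times, yet PSA is required by eligibility and imaging is planned at Time 0. IPSS sits in the very same sentence and has a pre-treatment value. If the study is truly retrospective, a baseline IIEF-5 may already be in the files. This stands to the extent that one cannot say no baseline exists, only that the protocol neither requires nor mentions one. It does not rescue the IIEF-5, because no other provision guarantees it as eligibility guarantees PSA and IPSS.

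Second, the protocol never promises a change score or a claim of preserved function, and the cited rates after radiotherapy and surgery are background, not planned comparators. That is literally true, and post-treatment levels remain describable. But assessing effectiveness on function needs some reference, and none is given.

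Third, the outcome definition could be left to a statistical analysis plan, and none was available. A fair point about the definition; but an analysis plan cannot create a measurement that was not taken, and the assessment schedule belongs in the protocol.

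Fourth, the illustrative percentages rest on assumed counts and include extreme cases. This is correct. The finding depends on the missing time point and not on those figures.

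**Conclusion.** The concern holds. The protocol specifies no pre-treatment IIEF-5 or other erectile measure and describes no comparator, so a study run exactly as written cannot say how much erectile dysfunction followed ablation. In the illustration with 15 of 30 men affected at 12 months and no recovery, the proportion with new dysfunction could lie anywhere from 0% to 50%, depending on a baseline count nobody is told to record.

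The conclusion rests on the text alone and assumes that no unstated practice fills the gap. If the files do hold a pre-treatment score for every man, the data problem disappears and the protocol need only say so. The oncological aim and the definition of treatment success are unaffected. For IPSS the gap is one of documentation: the screening score must exist but is not named as the baseline. The gap should be closed before further patients are treated, because it cannot be closed afterwards.

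**What to change.** 1. For men not yet treated, add the IIEF-5 to the pre-procedural (Time 0) evaluation, and state that the screening IPSS is kept as the baseline value.
2. Define the functional outcome as within-patient change from baseline to 3, 6 and 12 months, and report new erectile dysfunction among men potent at baseline. The detail may go in the analysis plan.
3. Reconcile the retrospective label with the consent statement. For men already treated, state whether a pre-treatment IIEF-5 is on file and report how many of the 30 have one.
4. Where none is on file, limit the erectile-function conclusion to post-treatment levels and make no claim of preservation or change.

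For untreated men the cost is one protocol sentence and a few minutes of questionnaire each. For treated men it is a file check and, where no score is found, a narrower claim.
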